7.3 Adverse Events—Causality Rating

The causality of each adverse event should be assessed and classified by the Investigator as "related" or "not related." An event is considered related if there is "a reasonable possibility" that the event may have been caused by the product under investigation (i.e., there are facts, evidence, or arguments to suggest possible causation).

Guidelines for "Related" Events

- There is clear evidence to suggest a causal relationship, and other possible contributing factors can be ruled out.
- There is evidence to suggest a causal relationship, and the influence of other factors is unlikely.

- There is some evidence to suggest a causal relationship (e.g., the event occurred within a reasonable time after administration of the study drug). However, the influence of other factors may have contributed to the event (e.g., the subject's clinical condition, other concomitant events).

Guidelines for “Not related” Events

- There is little evidence to suggest there is a causal relationship. There is another reasonable explanation for the event.
- An adverse event will be considered “not related” to the use of the product if any of the following tests are met:
 - An unreasonable temporal relationship between administration of the product and the onset on the AE (e.g., the event occurred either before, or too long after administration of the product for it to be considered product-related)
 - A causal relationship between the product and the AE is biologically implausible (e.g., death as a passenger in an automobile accident)
 - A clearly more likely alternative explanation for the AE is present (e.g., typical adverse reaction to a concomitant drug and/or typical disease-related event)

Consider the Following When Assessing Causality

- Temporal associations between the agent and the event
- Effect of dechallenge and/or rechallenge
- Compatibility with known class effect
- Known effects of concomitant medications
- Preexisting risk factors
- A plausible mechanism
- Concurrent illnesses

7.4 Serious Adverse Events and Unexpected Adverse Events

In addition to the severity rating, each AE is to be classified by the Investigator as “serious” or “not serious.” The seriousness of an event is defined according to the applicable regulations and generally refers to the outcome of an event. An SAE is one that meets one or more of the following:

- Is fatal
- Is life-threatening

- Is persistent or significantly incapacitating or causes substantial disruption of the ability to conduct normal life functions
- Requires inpatient hospitalization
- Prolongs existing hospitalization
- Is a congenital anomaly or birth defect
- Is an important medical event that may jeopardize the subject and/or may require medical or surgical intervention to prevent one of the outcomes listed above

Definition of Life-threatening

An adverse event or suspected adverse reaction is considered "life-threatening" if, in the view of either the Investigator or Sponsor (and/or designee), its occurrence places the subject at immediate risk of death. It does not include an adverse event or suspected adverse reaction that, had it occurred in a more severe form, might have caused death.

Definition of Hospitalization

Hospitalization is defined by the Sponsor as a full admission to the hospital for diagnosis and treatment. This includes prolongation of an existing inpatient hospitalization.

Examples of visits to a hospital facility that do not meet the serious criteria for hospitalization include:

- Emergency room visits that last for a period of <24 hours and do not result in a full hospital admission
- Outpatient surgery
- Preplanned or elective procedures ([Section 7.4.1](#))
- Protocol procedures

The above events would not be reported as SAEs unless the event triggering the hospital visit is an SAE as defined by other SAE criteria such as life-threatening, results in persistent or significant disability/incapacity or as per medical judgment of the Investigator.

Any other event fulfilling the definition of serious that develops as a result of the in-hospital procedure or extends the hospital stay is an SAE.

Definition of Disability

Disability is defined as a persistent or significant incapacity or substantial disruption of the ability to conduct normal life functions.

Definition of Medically Significant

Important medical events (medically significant events) that may not result in death, be life-threatening or require hospitalization may be considered to be an SAE when, based upon appropriate medical judgment, they may jeopardize the subject and/or may require medical or surgical intervention to prevent one of the outcomes listed in this definition. Examples of such events are a new diagnosis of cancer, intensive treatment in an emergency room or at home for allergic bronchospasm, or convulsions that do not result in hospitalization, or development of drug dependency or drug abuse.

An SAE may also include any other event that the Investigator or medical monitor judges to be serious, or that suggests a significant hazard, contraindication, side effect, or precaution.

Definition of Suspected Adverse Reactions

Suspected adverse reaction is considered any AE for which there is a reasonable possibility that the drug caused the AE.

Definition of Unexpected

An AE or suspected adverse reaction is considered “unexpected” if it is not listed in the Investigator Brochure or is not listed at the specificity or severity that has been observed. “Unexpected,” as used in this definition, also refers to adverse events or suspected adverse reactions that are mentioned in the Investigator Brochure as occurring with a class of drugs or as anticipated from the pharmacological properties of the drug, but are not specifically mentioned as occurring with the particular drug under investigation.

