8.10.8. Other Efficacy Analyses

8.10.8.1. Cardiac Hospitalizations

Hospitalization reason will be coded using MedDRA version 19.0. Any adverse event with a preferred term in the broad standardized MedDRA query (SMQ) definition of Cardiac Failure or in the SMQ definition of Cardiac Arrhythmias that results in hospitalization will be counted as a Cardiac Hospitalization.

Time to first cardiac hospitalization admission will be calculated in days as the date of first cardiac hospitalization admission minus the date of first study drug infusion plus 1. Subjects who do not experience an event will be censored at the date of last contact. NEOD001 will be compared to placebo using the same methods described in Section 8.10.7.1. In addition, the time to recurrent cardiac hospitalization, i.e., time to next cardiac hospitalization after the first, will be analyzed in the same manner.

The number of cardiac hospitalizations per subject over the course of the study will be summarized both as a continuous and categorical variable by treatment group. A Poisson regression model will be fit using the continuous number of cardiac hospitalizations as the dependent variable, the total time in study as the offset variable, and treatment group as a factor. The number of cardiac hospitalizations per subject will be categorized as 0, 1, and ≥ 2 . The categorical variable will be analyzed using a CMH test stratified by the randomization stratification factors. The number and percentage, with associated two-sided 95% CIs, of subjects in each category will be presented by treatment group. An ordinal logistic regression

will be performed with categorical number of hospitalizations (0, 1, and ≥ 2) as the dependent variable and factors for treatment group and randomization strata.

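### SAP 8.10.8.1 counts cardiac hospitalizations per adverse event and has no rule merging events of one admission, so one stay with two qualifying events can count as two

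*Protocol*

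**What the plan says.** SAP 2.3.4.8.1 lists the frequency of cardiac hospitalizations over the study as an exploratory efficacy endpoint. SAP 8.10.8.1 defines and analyses it.

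- **Counting rule.** Any adverse event with a preferred term in the broad Cardiac Failure SMQ or in the Cardiac Arrhythmias SMQ "that results in hospitalization will be counted as a Cardiac Hospitalization".
- **Coding.** "Hospitalization reason will be coded using MedDRA version 19.0".
- **First event.** The time is "calculated in days as the date of first cardiac hospitalization admission" minus the date of first infusion, plus one.
- **Recurrence.** The "time to next cardiac hospitalization after the first, will be analyzed in the same manner".
- **Count.** "A Poisson regression model will be fit using the continuous number of cardiac hospitalizations as the dependent variable", with total time in study as offset and treatment group as a factor. No scale parameter or robust variance is mentioned.
- **Categories.** The number per subject is grouped as 0, 1 and 2 or more, and analysed by a stratified CMH test and by ordinal logistic regression.

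Protocol 7.4 defines hospitalization for judging seriousness as a full admission and adds: "This includes prolongation of an existing inpatient hospitalization". It also says that another event that meets the definition of serious and "extends the hospital stay is an SAE". SAP 8.10.8.1 does not refer to Protocol 7.4.

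**The concern.** The section uses two units. The counting sentence works on adverse events. The coded reason and the date of the first event work on admissions. Nothing links several events to one stay.

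A programmer who follows the counting sentence will score two hospitalizations when heart failure and an arrhythmia are both recorded as leading to the same admission. Such co-recording is foreseeable here: inclusion criterion 4 requires past or present signs and symptoms of heart failure, and exclusion criterion 6 permits atrial fibrillation with a controlled ventricular rate.

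What is at stake is the meaning of the endpoint. The Poisson rate, the 0/1/2-or-more comparison and the time to the next hospitalization would partly measure how many cardiac terms were recorded per stay, rather than how often subjects were admitted. If the rule is settled only after unblinding, someone must choose between two defensible counts with the results in view.

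**Working it through.** **No figure to reproduce.** The documents give no expected rate, event count or power for cardiac hospitalizations. The check is a reading of the rule, then an illustration under stated assumptions.

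**Step 1: apply the rule to one stay.** A subject is admitted once, and heart failure and an arrhythmia are both recorded as resulting in hospitalization.

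| Analysis in SAP 8.10.8.1 | Counting events | Counting admissions |
|---|---|---|
| Contribution to the Poisson count | 2 | 1 |
| Category | 2 or more | 1 |
| Time to first | admission date | admission date (same) |
| Time to next | no new admission date: undefined, or dated within the stay | none; censored |

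This does not need the prolongation sentence. If Protocol 7.4 were carried over, a cardiac event arising in hospital and extending the stay could be a further source of extra counts.

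**Step 2: is merging a general convention of the SAP?** No. Where the SAP wants repeats collapsed it says so: SAP 9.1 and 9.1.1 count one infusion when several start times fall on one day. SAP 8.10.8.1 has no counterpart.

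**Step 3: size under assumptions.** Let admissions per subject be Poisson with mean *m*, with equal follow-up, and let a share *q* of admissions carry a second qualifying event. Neither value is in the documents. I take *m* = 0.2 to 0.5 and *q* = 0.2 to 0.4.

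*Mean count.* Inflation = 1 + *q*, so 1.2 to 1.4.

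*Share of subjects in the category of 2 or more.*
- By admissions: 1 − e^(−m) − m·e^(−m).
- By events: 1 − e^(−m) − m·e^(−m)·(1 − q). The increase is q·m·e^(−m), all from subjects with a single admission.
- Example, *m* = 0.2 and *q* = 0.2: 1 − 0.8187 − 0.1637 = 0.0175 (unrounded); increase 0.2 × 0.1637 = 0.0327; total 0.0503.

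| *m* | By admissions | By events, q = 0.2 | By events, q = 0.4 | Of those at 2 or more, share with one admission |
|---|---|---|---|---|
| 0.2 | 1.8% | 5.0% | 8.3% | 65% to 79% |
| 0.35 | 4.9% | 9.8% | 14.7% | 50% to 67% |
| 0.5 | 9.0% | 15.1% | 21.2% | 40% to 57% |

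*Overdispersion.* Each admission yields 1 + Bernoulli(*q*) events, so the per-subject mean is m(1 + q) and the variance is m(1 + 3q). Variance/mean is φ = (1 + 3q)/(1 + q). With no treatment effect, an unadjusted Poisson Wald test at nominal two-sided 0.05 has true level 2[1 − Φ(1.96/√φ)].

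| *q* | φ | Level by formula | Level by simulation |
|---|---|---|---|
| 0.10 | 1.18 | 0.071 | 0.064-0.069 |
| 0.25 | 1.40 | 0.098 | 0.091-0.095 |
| 0.50 | 1.67 | 0.129 | 0.123-0.125 |

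The simulation used 65 subjects per arm (half of the planned maximum of 130), 40,000 replicates and *m* = 0.2, 0.3 and 0.5. Counting each admission once gave 0.043 to 0.048. That recovery depends on admissions themselves being Poisson, which is also assumed.

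**Step 4: what is not affected.** The expected rate ratio is m₁(1 + q₁)/[m₀(1 + q₀)]. With q₁ = q₀ the inflation cancels, so there is no bias in the ratio. Time to first cardiac hospitalization uses the admission date, so a second event in the first admission does not change it.

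**The case against.** The strongest reply is that the section does not clearly intend to count events. It codes a reason for hospitalization and dates the first one by admission, so the adverse event sentence can be read as the test for whether a hospitalization is cardiac. Protocol 7.4.3 also asks that a serious event resulting from disease progression be reported as the diagnosis that best describes it, which discourages several terms for one episode. This stands as evidence that the section is mixed. It does not supply a merging rule: the counting sentence still attaches the count to each qualifying event, and 7.4.3 does not exclude two diagnoses in one stay.

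A reader might infer that the plan prescribes a false recurrence. The documents do not support that. Because the first event is dated by admission and "time to next cardiac hospitalization after the first" is analysed in the same manner, a second event in the same stay has no new admission date. The plan permits a recurrence within the stay but does not require one.

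A reader might also infer that prolongation is counted because Protocol 7.4 includes it. That definition serves SAE reporting. The SAP does not cite it, and Protocol 7.4 itself lists requiring admission and prolonging a stay as separate criteria for seriousness. The protocol text is not at fault; the gap is in the SAP.

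Finally, the numbers follow from assumed inputs, and the documents give no reason to expect co-recording to differ between arms in a double-blind trial. Both limits stand.

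**Conclusion.** The concern holds for the counting unit. Followed literally, SAP 8.10.8.1 scores one admission with two qualifying events as two cardiac hospitalizations. This affects the absolute rate, the 0/1/2-or-more categories and the variance of the Poisson count, and leaves the time to the next hospitalization without a usable definition for a second event in the same stay.

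The real size is unknown. The 1.2 to 1.4 inflation rests on an assumed second-event share of 20% to 40%, and the category shifts rest also on assumed admission rates. If the share differed by arm, the rate ratio would be biased as well, but nothing in the documents shows that it would.

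The consequence is limited. The endpoint is exploratory and lies outside the testing sequence in SAP 8.6, so no primary or key secondary conclusion depends on it. It is worth settling before unblinding because the stated rule can give a wrong count and the correction is cheap.

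**What to change.** Amend SAP 8.10.8.1 as follows.

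1. Make the distinct admission, from admission date to discharge, the unit. Count it once if any adverse event in either SMQ resulted in it, and date it by the admission date, as the SAP already does for the first event.
2. Require discharge and a new admission for a recurrent cardiac hospitalization.
3. State that an event that only prolongs an admission already counted adds nothing.
4. State whether a cardiac event that prolongs a non-cardiac stay counts.
5. Apply the same unit to the Poisson model, the 0/1/2-or-more analyses and the time to next hospitalization.

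The cost is SAP wording and programming. The planned analyses already rely on admission dates; discharge dates are needed to separate one stay from the next, and their availability should be confirmed.

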7.4.1 Elective Procedures and Surgeries

For the purposes of this protocol, the following conventions will apply for SAE reporting of elective procedures, and surgeries:

- A prescheduled elective procedure or a routinely scheduled treatment is not to be considered an SAE, even if the subject is hospitalized, provided the site stipulates that:
 - The condition requiring the prescheduled elective procedure or routinely scheduled treatment was present before and did not worsen or progress between the subject’s consent to participate in the clinical trial and the time of the procedure or treatment
 - The prescheduled elective procedure or routinely scheduled treatment is the sole reason for admission and intervention
- An untoward medical event occurring during the prescheduled elective procedure or routinely scheduled treatment should be recorded as an AE or a SAE. Any concurrent medications should also be recorded on the eCRF.

7.4.2 Other Reportable Information

In addition, and for the purposes of monitoring, any occurrence of exposure through lactation and any pregnancy (with or without an AE) of a female subject or partner of a male subject should be reported, regardless of seriousness, according to the directions in [Section 7.4.4](#). Any subject who becomes pregnant during the study must be withdrawn from study drug treatment, and will be followed to term.

7.4.3 Disease Progression and Death

Disease progression (including progression of hematologic condition and/or organ dysfunction of AL amyloidosis, and death due to disease progression) is generally recorded as part of the efficacy evaluation and should not be reported as a specific AE or SAE term. When an AE resulting from disease progression meets the requirements to be considered serious, the SAE verbatim term should be reported as the diagnosis that best describes the event rather than as “disease progression.” For instance, a subject with pleural effusion presents with shortness of breath. The cause of the shortness of breath is a pleural effusion resulting from disease progression. The event term may be reported as “pleural effusion” instead of disease progression.

Death should not be reported as an SAE term, but as a clinical outcome of a specific SAE. The cause of death, reported on a source document such as the Death Certificate or autopsy report, should be used as the event term for the SAE. For example, in a subject with acute heart failure that results in death, the SAE is reported as “acute heart failure” with an outcome of “death.”

7.4.4 Serious Adverse Events—Reporting

It is the responsibility of the Investigator to report SAEs to the Sponsor or its designee within 24 hours of awareness of the event or safety information, whether initial or follow-up.

All SAEs must be reported immediately (within 24 hours of awareness) to the Sponsor or its designee (see Study Manual for details). Do **not** delay in the reporting of a suspected SAE in order to obtain additional information. Any additional information, if collected, can be reported to the Sponsor or its designee as a follow-up to the initial report. SAEs will be reported using the SAE forms provided as part of the Study Manual. Please remember to give details of the subject identification number or other appropriate terminology and ensure the narrative is comprehensive and includes a chronology and assessment of the event.

Reporting of SAEs to the IRB/IEC will be done in compliance with the standard operating procedures and policies of the IRB/IEC and with applicable regulatory requirements. Adequate information must be obtained by the Sponsor or its designee showing that the IRB/IEC was properly and promptly notified as required. Please refer to the Study Manual for details on reporting SAEs.

The Investigator is encouraged to discuss any AEs with the Sponsor Medical Monitor for which the issue of seriousness is unclear or questioned. Contact information for the Medical Monitor is listed on the Team Roster in the Study Manual.

The reporting period for SAEs is the period from signing of the ICF through 30 days after the last administration of study drug or last study visit, whichever is later. SAEs reported to the Investigator outside of this reporting period will be reported to the Sponsor or its designee only if, in the judgment of the Investigator, there is “a reasonable possibility” that the event may have been caused by the product.

All SAEs will continue to be followed until the end of the study or until such events have resolved or the Investigator, in conjunction with the Sponsor or its designee, deems them to be chronic or stable.

8 STATISTICAL METHODS AND CONSIDERATIONS

A statistical analysis plan, providing details about the specific planned analyses and hypothesis tests, will be prepared and approved by the Sponsor prior to study database lock and unblinding of double blind subject treatment assignments.

Endpoints are listed in [Section 3.2](#).

8.1 Analysis Populations

The Intent-to-Treat (ITT) Population will include all randomized subjects who receive any amount of study drug (NEOD001 or placebo). The ITT Population will be the primary population used for efficacy analyses. Treatment assignment will be based on the randomized treatment.

The Safety Population will include all subjects who receive any amount of study drug (NEOD001 or placebo). The Safety Population will be the primary population used for safety analyses. Treatment assignment will be based on the randomized treatment.

Efficacy Subset Populations:

The Renal Evaluable Population will include subjects who had renal involvement, i.e., proteinuria >0.5 g/24 hours (measured by 24-hour urine total protein excretion), at baseline and at least one postbaseline assessment of proteinuria.

The Peripheral Neuropathy Evaluable Population will include subjects who had peripheral nerve involvement at baseline (only if the subject had ascending sensorimotor neuropathy due to AL amyloidosis etiologies answered as yes) and had a baseline Neuropathy Impairment Score–Lower Limbs (NIS-LL) total score of 2 or greater and at least one postbaseline NIS-LL total score.

The Hepatic Evaluable Population will include subjects who had hepatic involvement defined as $>1.5 \times$ ULN alkaline phosphatase at baseline and at least one postbaseline assessment of alkaline phosphatase.

8.2 Analysis of Study Population and Subject Characteristics

Enrollment, important protocol deviations, and discontinuations from the study will be summarized.

Demographic and baseline characteristics, such as age, sex, race, and weight at Screening will be summarized using means, standard deviations, medians, ranges for continuous variables, and proportions for categorical variables.

Study drug administration data will be listed and any dose modifications will be flagged. Study drug exposure will be summarized using total number of infusions received, percentage of expected infusions, total dose interruptions and reductions, and dose strength.

8.3 Analysis of Efficacy Endpoints

8.3.1 Primary Efficacy Analysis

The NT-proBNP best response rates in the two arms will be compared using the Cochran-Mantel-Haenszel (CMH) test at the $\alpha=0.05$ (two-sided) level of significance. The analysis will be stratified by the randomization stratification factors.

